10.3 STATISTICAL ANALYSES

10.3.1 Analysis of the Primary Endpoints

The 90% and 95% confidence intervals will be constructed around the observed fraction of patients with grade 3+ neurologic toxicity, and will be reported along with the observed incidence. If 5/45 are noted to have grade 3+ neurologic toxicity, the exact two-sided 90% CI bound extends from 4.5% to 22.0%, thus confirming that this rate of toxicity is likely to exceed 5%, and is consistent with as high as 22%.

As an early stopping rule for toxicity for the first 20 patients: if 4 patients are found to have grade 3+ neurologic toxicity in the first two completed cycles of treatment, no further patients will be enrolled. As soon as this can be determined, since the lower 80% one-sided confidence bound around 4/20 is 11.7%, which, being greater than 10%, would be considered demonstration of excessive toxicity. In fact, the lower 80% bounds range from 67% for observing 4 patients with grade 3+ neurologic toxicity in the first 4 patients to 12% for observing 4 patients with grade 3+ neurologic toxicity in 20 patients.

The rates of VGPR+CR and CR alone will also be estimated and reported. These rates are expected to be fairly high. Two-sided 95% confidence interval bounds will be formed around each of these measures.

In order to allow for a small number of inevaluable patients, the accrual ceiling will be set at 50.

It is anticipated that 2-3 patients per month may enroll on this trial; thus, 2 years is anticipated as the accrual period for this study.

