10.2 SAMPLE SIZE DETERMINATION

The sample size on which the trial will be based will be that necessary to demonstrate if the rate of grade 3 or worse neurologic toxicity is lower than 10%, or if it could be consistent with a rate which is greater than 10%, in which case it would be considered excessive.

We will plan to enroll a total of 45 evaluable patients in a single cohort and score each patient for the development of grade 3 or worse neurologic toxicity in the first two completed cycles of treatment. If we enroll 45 patients and if 5 or more have grade 3 or worse neurologic toxicity,

then the probability that the true rate of grade 3+ neurologic toxicity is 5% is 7.3% while the probability that the true rate of grade 3+ neurologic toxicity is 15% is 82.5%. Thus, the appearance of 5 or more patients with grade 3+ neurologic toxicity in 45 patients will provide evidence that the true rate of toxicity is consistent with 15%, and will be considered excessive.

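### Section 10.3.1 reads the exact 90% interval for 5/45 (4.5% to 22.0%) as confirming that the rate is likely above 5%, but that interval contains 5%

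*Combined protocol and SAP*

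**What the plan says.** Section 10.2 sets the size and the rule: "We will plan to enroll a total of 45 evaluable patients in a single cohort", and "the appearance of 5 or more patients with grade 3+ neurologic toxicity in 45 patients will provide evidence" that the true rate is consistent with 15%, which the plan calls excessive. For the low rate it gives this figure: "then the probability that the true rate of grade 3+ neurologic toxicity is 5% is 7.3" percent. The companion figure for a true rate of 15% is 82.5%. The limit above which the design regards the rate as excessive is 10% (sections 3.1 and 10.2).

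Section 10.3.1 then says what will be reported: "The 90% and 95% confidence intervals will be constructed around the observed fraction of patients with grade 3+ neurologic toxicity", alongside the observed incidence. It works through the result at the cutoff. "If 5/45 are noted to have grade 3+ neurologic toxicity", the plan says, "the exact two-sided 90% CI bound extends from 4.5% to 22.0%, thus confirming that this rate of toxicity is likely to exceed 5" percent, and it adds that the rate could be as high as 22%.

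The next paragraph of 10.3.1 interprets the early stopping rule. There the lower one-sided 80% bound for 4/20 is 11.7%, and the plan counts this as showing excessive toxicity because the bound is above 10%.

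**The concern.** A confidence interval supports a claim that a rate exceeds some value when its lower limit lies above that value. Here the printed lower limit is 4.5% and the value is 5%, so 5% is one of the rates the interval leaves open. The sentence nevertheless presents the claim as following from the interval.

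The stopping-rule paragraph uses the proper logic: a lower bound of 11.7% is set against a reference of 10% and lies above it. The 5/45 sentence draws the same kind of conclusion from a bound on the wrong side of its reference.

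What is at stake is the interpretation of the primary endpoint at the one count where it is most delicate, the smallest number of events that triggers the excessive-toxicity conclusion. A report that took its wording from this sentence would speak of confirmation beside two intervals that both include 5%.

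**Working it through.** **Inputs.** n = 45, cutoff 5 or more, low rate 5% and high rate 15% (section 10.2). Worked example 5/45, exact two-sided 90% interval, with 90% and 95% intervals to be reported (section 10.3.1). Limit for excessive toxicity 10% (sections 3.1 and 10.2).

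**1. Reproduce the plan's interval.** The exact (Clopper-Pearson) limits for x events in n are:
- lower = the α/2 quantile of Beta(x, n − x + 1)
- upper = the 1 − α/2 quantile of Beta(x + 1, n − x)

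For 5/45 at 90%, the lower limit is the 0.05 quantile of Beta(5, 41) = 4.48%. The upper limit is the 0.95 quantile of Beta(6, 40) = 21.95%. This matches the printed 4.5% and 22.0%. The point estimate is 5/45 = 11.1%.

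**2. The second planned interval.** At 95%, the 0.025 quantile of Beta(5, 41) = 3.71% and the 0.975 quantile of Beta(6, 40) = 24.05%.

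**3. Compare with the reference rates.**

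| Events/45 | 90% lower limit | 95% lower limit | Above 5%? |
|---|---|---|---|
| 5 | 4.48% | 3.71% | neither |
| 6 | 5.97% | 5.05% | both |

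Both intervals at 5/45 also contain 10%.

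**4. Cross-check with section 10.2.** For X ~ Binomial(45, p), P(X ≥ 5) = 1 − Σ(k = 0 to 4) C(45, k) p^k (1 − p)^(45 − k).
- p = 0.05: 0.0729 (the plan's 7.3%)
- p = 0.15: 0.8252 (the plan's 82.5%)

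Section 10.2 words these as probabilities about the true rate. They reproduce as probabilities of 5 or more events given that rate, and are read that way here. At 5/45 the first figure is the one-sided exact p-value against 5%, so p = 0.073. The one-sided confidence that the rate exceeds 5% is 1 − 0.073 = 0.927, short of the 0.95 carried by each limit of a two-sided 90% interval. Sections 10.2 and 10.3.1 therefore agree numerically that 5% is not excluded.

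**5. Check the stopping-rule comparison.** The 0.20 quantile of Beta(4, 17) is 11.70%, as printed, and does lie above 10%.

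**6. Sensitivity to the interval method.** The 90% lower limits for 5/45 by other methods are Wilson 5.5%, Blaker 5.3%, Agresti-Coull 5.2%, Jeffreys 5.2%, mid-P 5.05% and Wald 3.4%. Several lie just above 5%. The plan, however, specifies an exact interval, and its printed 4.5% is the Clopper-Pearson limit.

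**The case against.** The strongest reply is that the plan hedges. It says the rate is likely to exceed 5%, not that it does. With an estimate of 11.1%, more than twice 5%, and 92.7% one-sided confidence, that is a fair informal statement. This stands: a reader might infer that the plan's conclusion is false or that a figure is wrong, and the documents support neither. Every printed number reproduces. The hedge does not rescue the inference, though, because the interval is put forward as what confirms the statement.

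A second reply is that 5% decides nothing. It is only the low rate used for the operating characteristics; the limit is 10%, and the operative rule is the count of 5 in section 10.2. This also stands. A reader might infer that the decision rule is undermined because 5/45 excludes neither 5% nor 10%. But the rule is justified by tail probabilities at 5% and 15%, not by an interval excluding either value, and those probabilities are correct.

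A third reply is that the sentence is a planning illustration, not mandated report text, and that the printed intervals would let any reader see that 5% is included. That is fair. It is also not the only interpretive statement in the section, since the stopping rule is interpreted too.

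Finally, the case may be remote. At a true rate of 5%, exactly 5 events in 45 has probability 4.9% before any data. Section 1.2.10 reports no grade 3 or higher neuropathy in the first 20 patients. If neuropathy stands in for neurologic toxicity (an assumption, as the terms differ), 5/45 needs 5 events in the other 25. At a 5% rate this has probability C(25, 5) × 0.05^5 × 0.95^20 = about 0.6%. Section 13.1.1 also refers to recruitment and treatment in the past tense. These points limit the practical weight of the correction; they do not make the sentence right.

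**Conclusion.** The point holds as an error of interpretation in one sentence. At 5/45 the exact 90% interval (4.48% to 21.95%) and the planned 95% interval (3.71% to 24.05%) both contain 5%, so neither confirms a rate above it. The shortfall is small: the 90% lower limit misses 5% by about half a percentage point (5 − 4.48 = 0.52), the one-sided exact p-value is 0.073, and one more event (6/45) takes both lower limits past 5%.

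The conclusion rests on the Clopper-Pearson method, which the plan's own printed limits identify, and on reading a two-sided 90% interval as carrying 5% in each tail. It does not extend to the arithmetic, the sample size, the 5-of-45 rule or its stated tail probabilities, all of which are unaffected.

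**What to change.** Replace the 5/45 sentence in section 10.3.1 with:

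> If 5/45 are noted, the exact two-sided 90% CI is 4.5% to 22.0%; it includes both 5% and the 10% limit, so 5/45 meets the pre-specified cutoff for excessive toxicity but does not by itself exclude a 5% rate (one-sided exact p = 0.073). The 90% and 95% lower limits first exceed 5% at 6/45.

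Do not add a two-sided 80% interval to restore agreement with the cutoff. At 5/45 it runs from 5.5% to 19.6% and would exclude 5%, but the level would have been picked to get that exclusion, and the report would carry a third interval.

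The cost is one sentence, with no change to the sample size, the cutoff or the planned intervals. The downside is that the stated conclusion at the cutoff becomes slightly weaker.

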10.3.2 Analysis of the Secondary Endpoints

Secondary endpoints are to estimate overall response rates (ORR) according to International Myeloma Working Group criteria after 8 cycles(31), progression free survival (PFS), duration of response and overall survival. Progression free survival, duration of response and overall survival will be estimated using the Kaplan-Meier method and reported along with 95% confidence intervals at appropriate time points.

A number of correlative studies will be performed in order to assess carfilzomib in vitro biological activity and investigate minimal residual disease in MM. Minimal residual disease will be further explored using multi-parametric flow cytometry and PET-CT imaging.

11 COLLABORATIVE AGREEMENTS

11.1 AGREEMENT TYPE

11.1.1 Cooperative Research and Development Agreement (CRADA)

The following CRADAs are associated with this protocol: Amgen, Inc. (formerly directly with Onyx Pharmaceuticals), Inc. (#02695) for Carfilzomib; Celgene Corporation (#02696) for Lenalidomide.

11.1.2 Material Transfer Agreements (MTA)

11.1.2.1 Memorial Sloan Kettering Cancer Center (MSKCC)

An MTA was executed before any of the samples described in Section 5 were shipped to [name], PhD at Memorial Sloan Kettering Cancer Center (MSKCC #37998). [name] will use samples for analyses of the causation, diagnostics and prognostics, and natural history of multiple myeloma and its precursor conditions. Additionally, the samples may be used for analyses of related hematologic malignancies and their precursors states (including chronic lymphocytic leukemia and monoclonal B-cell lymphocytosis (MBL); Waldenstrom's macroglobulinemia and IgM MGUS), as well as myeloproliferative neoplasms.

[name] is a former NIH staff member and PI/AI on this study whose ongoing role was originally intended to be covered by an NIH FWA Coverage Agreement to continue work on this study. In reviewing the samples sent to [name], it has been determined that samples received by him were coded in such a manner that it would not be possible for him to identify the subjects from which the samples were obtained. [name] also does not have any access to the code key to identify the subjects. Therefore, with Amendment P, [name] involvement on study has been updated to a Non-NIH Collaborator as he does not have access to patient identifiers.

11.1.2.2 Food and Drug Administration (FDA)

An MTA will be executed to allow the samples described in Section 5 to be shipped to the Office of Biotechnology at the FDA as part of the collaborative effort. The MTA will be a global CCR MTA (#43656) to include multiple protocols; however, [name] will be the responsible PI regarding the multiple myeloma protocols both at the NIH and FDA site.

12 HUMAN SUBJECTS PROTECTIONS

12.1 RATIONALE FOR SUBJECT SELECTION

MM is an almost always incurable plasma cell neoplasm that comprises approximately 10% of all hematologic malignancies. MGUS, SMM, and MM increase in incidence with age. According to SEER statistics, from 2003-2007, the median age at death for myeloma is 75 years of age.⁽¹⁾ Incidence rates of myeloma is higher among Blacks compared to Caucasians, affecting 14.3 black males per 100,000 males and 10.0 black females per 100,000 females compared to 6.7 white males per 100,000 males and 4.1 white females per 100,000 women.⁽¹⁾ Despite this, MM affects all genders and races. As such, we expect that the majority of patients enrolled in this trial will be older adults of either gender or race. MM patients enrolled on this study will consist of patients referred to and screened at the NIH Clinical Center. There will be no subject selection bias with regard to gender, ethnicity, or race. This protocol excludes lactating and pregnant women from receiving this investigational drug to avoid any possible risks to the fetus or newborn.

12.2 PARTICIPATION OF CHILDREN

Pediatric patients with SMM are extremely rare. Patients under the age of 18 are excluded from this study because inclusion of a rare younger patient will not provide adequate generalizable information to justify their inclusion in this study

12.3 PARTICIPATION OF SUBJECTS UNABLE TO GIVE CONSENT

Adults unable to give consent are excluded from enrolling in the protocol. However, re-consent may be necessary and there is a possibility, though unlikely, that subjects could become decisionally impaired. For this reason and because there is a prospect of direct benefit from research participation (Section 12.4), all subjects \geq age 18 will be offered the opportunity to fill in their wishes for research and care, and assign a substitute decision maker on the “NIH Advance Directive for Health Care and Medical Research Participation” form so that another person can make decisions about their medical care in the event that they become incapacitated or cognitively impaired during the course of the study. Note: The PI or AI will contact the NIH Ability to Consent Assessment Team (ACAT) for evaluation as needed for the following: an independent assessment of whether an individual has the capacity to provide consent; assistance in identifying and assessing an appropriate surrogate when indicated; and/or an assessment of the capacity to appoint a surrogate. For those subjects that become incapacitated and do not have pre-determined substitute decision maker, the procedures described in MAS Policy 87-4 4 and NIH HRPP SOP 14E for appointing a surrogate decision maker for adult subjects who are (a) decisionally impaired, and (b) who do not have a legal guardian or durable power of attorney, will be followed.

12.4 RISKS/BENEFITS ANALYSIS

Currently, MM is an incurable malignancy with frequent complications of skeletal fractures, anemia, renal failure and hypercalcemia. Combination use of novel agents, such as proteasome inhibitors, have significantly prolonged survival in this disease population. However, toxicity from bortezomib has impacted patients with frequent episodes of debilitating neuropathy. Carfilzomib, a new-generation proteasome inhibitor, has been tested in phase 1 trials in combination with lenalidomide and dexamethasone.

Such combinations seem to be well-tolerated with minimal toxicity and significant benefit. The most recent phase 1 trial in newly diagnosed MM patients has shown 100% PR or better in 19 patients with a median of 4 months administered. More importantly, this treatment protocol takes a unique approach to investigating minimal residual disease in MM by applying novel techniques such as multiparametric flow cytometry and FDG PET CT as it relates to traditional IMWG response criteria.

The procedures required to obtain samples/data for experimental purposes (venipuncture, urine collection, PET/CT scan, DW-MRI and bone marrow biopsy) are of limited risk to the patient. Although patients will suffer some additional pain or discomfort from the PET/CT scans, DW-MRI and annual bone marrow biopsies, clinical experience has shown that the medical risk is limited.

Adults who become unable to consent are allowed to remain on study because the protocol offers a prospect of direct benefit. The ongoing risks and benefits of participation for adults who become unable to consent are no different than those described for less vulnerable patients.

12.5 CONSENT PROCESS AND DOCUMENTATION

Informed consent will be obtained from all patients on this trial. There will be no minors enrolled < 18 years of age; therefore, assent is unnecessary. The informed consent contains all elements required for consent. In addition, the Principal Investigator or an associate investigator or

member of the research team will discuss the protocol in detail with the patient and will be available to answer all patient questions to allow the patient to give informed consent.

12.5.1 Telephone Re-consent

Telephone consent applies to instances of re-consent only. Telephone re-consent will be obtained and documented per OHSRP/IRBO and CCR policies and procedures.

13 PHARMACEUTICAL INFORMATION

13.1 CARFILZOMIB (IND # 112587)

13.1.1 Source

Carfilzomib was provided to investigator by Onyx Pharmaceuticals, Inc. under a CRADA. Onyx provided carfilzomib during the active recruitment and treatment of this study. However, ongoing communication and sharing of information, including updated risks for carfilzomib, is through an agreement with Amgen.

13.1.2 Toxicity

A comprehensive listing of all toxicities (i.e., very common, common, etc.) are listed in the informed consent document. The approved USPI may also be referenced for current information related to this agent.

Amendment P, new information from Amgen, Inc: As of July 2019, carfilzomib has been examined in approximately 11,000 people in a research setting. It has been found that carfilzomib can cause a reactivation of hepatitis B virus. Additionally, there have been 4 cases of Progressive Multifocal Leukoencephalopathy (PML) possibly linked to Carfilzomib

13.1.3 Formulation and Preparation

Carfilzomib for Injection will be provided as a lyophilized powder which, when reconstituted, contains 2 mg/mL isotonic solution of carfilzomib Free Base in 10 mM sodium citrate buffer (pH 3.5) containing 10% (w/v) sulfobutylether- β -cyclodextrin (SBE- β -CD, Captisol®). Lyophilized Carfilzomib for Injection is stored in a refrigerator at 2°C–8°C. Water for injection is the only acceptable solution for reconstitution. After addition of the appropriate amount of water for injection and vigorous mixing, the solution is administered as an IV infusion. Vials are for single use. A volume of carfilzomib appropriate for a patient's dose will be added to 5% Dextrose Injection (D5W) in a sufficient amount to yield a volume to administer 100 mL (qs. 100 mL) in a polyvinyl chloride or polyolefin container.

For clinical use, Carfilzomib products will contain excess drug-containing fluid to compensate for product container and administration set priming volumes.

Before dispensing Carfilzomib products from the Pharmacy, an administration set suitable for a portable pump (e.g., Gemstar set 13758-28) will be attached, the administration set tubing will be primed with drug-containing fluid, air will be purged from the tubing (but not the product container), and the administration set will be capped with a Luer locking cap.

Lyophilized Drug Product: Lyophilized Carfilzomib for Injection is an investigational therapeutic agent provided in a single-dose vial as a sterile, lyophilized powder in the following dosages:

- 25 mg Single-Use Glass Vial / 8 pk Carton
Each single-dose vial contains 25 mg of carfilzomib in a 20 mL labeled glass vial with an elastomeric stopper and Red flip-off lid. The product is supplied to the site in labeled

carton(s) containing eight (8) single-use vials/carton and is shipped and stored between 2°C - 8°C (36°F - 46°F). Remove the Red flip-off lid on the vial and aseptically add 12 mL of Water for Injection, USP to the lyophilized drug. Gently invert the vial multiple times and let stand to yield a clear solution containing 2 mg/mL carfilzomib. After reconstitution as instructed, a maximum total of 12.5 mL deliverable volume containing 25 mg of carfilzomib can be withdrawn from the vial.

- 45 mg Single-Use Glass Vial / 6 pk Carton

Each single-dose vial provides 45 mg of carfilzomib in a 30 mL labeled glass vial with an elastomeric stopper and Yellow flip-off lid. The product is supplied to the site in labeled carton(s) containing six (6) single-use vials/carton and is shipped and stored between 2°C - 8°C (36°F - 46°F). Remove the Yellow flip-off lid on the vial and aseptically add 22 mL of Water for Injection, USP to the lyophilized drug. Gently invert the vial multiple times and let stand to yield a clear solution containing 2 mg/mL carfilzomib. After reconstitution as instructed, a maximum total of 22.5 mL deliverable volume containing 45 mg of carfilzomib can be withdrawn from the vial.

- 60 mg Single-Use Glass Vial / 4 pk Carton

Each single-dose vial provides 60 mg of carfilzomib in a 50 mL labeled glass vial with an elastomeric stopper and Blue flip-off lid. The product is supplied in labeled carton(s) containing four (4) single-use vials/carton and is shipped and stored between 2°C - 8°C (36°F - 46°F). Remove the Blue flip-off lid on the vial and aseptically add 29 mL of Water for Injection, USP to the lyophilized drug. Gently invert the vial multiple times and let stand to yield a clear solution containing 2 mg/mL carfilzomib. After reconstitution as instructed, a maximum total of 30 mL deliverable volume containing 60 mg of carfilzomib can be withdrawn from the vial.

Inspection: The reconstituted drug solution in the vial should be a clear liquid. Inspect all vials for the presence of any suspended particles, particulate matter, discoloration or hazy solution prior to administration.

If the solution is not clear or particles exist in inspected vials, record the observation in the appropriate Drug Accountability Log and notify Amgen immediately.

- DO NOT USE THE DRUG.
- Place the vial(s) into a plastic bag labeled as "Quarantined" with the date.
- Store labeled quarantined drug in a temperature-monitored refrigerator and ensure they are physically segregated from the drug that is available for use.
- Amgen will instruct the clinical site on how to proceed with quarantined vial(s).

Calculation of Dose: Each dose will consist of Carfilzomib for Injection administered on a mg/m² basis, and should be based on the patient's actual calculated body surface area (BSA).

The BSA should be calculated based upon the institution's practice and method of calculation should remain consistent throughout a subject's participation in the trial.

Subjects with a BSA > 2.2 m² will receive a dose based upon a 2.2 m² BSA.

Dose adjustments do not need to be made for weight gains/losses of ≤ 20%.

